## 8.4.2 Method of Detecting AEs, SAEs, and Other Reportable Safety Events

Care will be taken not to introduce bias when detecting AEs and/or SAEs and other reportable safety events. Open-ended and nonleading verbal questioning of the participant is the preferred method to inquire about AE occurrence.

## 8.4.3 Follow-up of AE, SAE, and Other Reportable Safety Event Information

After the initial AE/SAE report, the investigator is required to proactively follow each participant at subsequent visits/contacts. All AEs, SAEs, and other reportable safety events, including pregnancy and exposure during breastfeeding, ECIs, cancer, and overdose will be followed until resolution, stabilization, until the event is otherwise explained, or the participant is lost to follow-up (as defined in Section 7.3). In addition, the investigator will make every attempt to follow all nonserious AEs that occur in randomized participants for outcome. Further information on follow-up procedures is given in Appendix 3.

#### 8.4.4 Regulatory Reporting Requirements for SAE

Prompt notification (within 24 hours) by the investigator to the Sponsor of SAE is essential so that legal obligations and ethical responsibilities towards the safety of participants and the safety of a study intervention under clinical investigation are met.

The Sponsor has a legal responsibility to notify both the local regulatory authority and other regulatory agencies about the safety of a study intervention under clinical investigation. The Sponsor will comply with country-specific regulatory requirements and global laws and regulations relating to safety reporting to regulatory authorities, IRB/IECs, and investigators.

Investigator safety reports must be prepared for SUSARs according to local regulatory requirements and Sponsor policy and forwarded to investigators as necessary.

An investigator who receives an investigator safety report describing an SAE or other specific safety information (eg, summary or listing of SAE) from the Sponsor will file it along with the IB and will notify the IRB/IEC, if appropriate according to local requirements.

## 8.4.5 Pregnancy and Exposure During Breastfeeding

Information in this section is not applicable since target population of this study is elderly participants.

# 8.4.6 Disease-related Events and/or Disease-related Outcomes Not Qualifying as AEs or SAEs

There are no disease-related events and/or disease-related outcomes not qualifying as AEs or SAEs in this study. Note that delirium as measured by DSM-5 should be reported as an AE eCRF as well, if the investigator assesses that the participant developed delirium as measured by DSM-5.

#### 8.4.7 Events of Clinical Interest

Selected serious and nonserious AEs are also known as ECIs and must be reported to the Sponsor.

Events of clinical interest for this study include:

1. An elevated AST or ALT lab value that is greater than or equal to 3X the upper limit of normal and an elevated total bilirubin lab value that is greater than or equal to 2X the upper limit of normal and, at the same time, an alkaline phosphatase lab value that is less than 2X the upper limit of normal, as determined by way of protocol-specified laboratory testing or unscheduled laboratory testing.\*

\*Note: These criteria are based upon available regulatory guidance documents. The purpose of the criteria is to specify a threshold of abnormal hepatic tests that may require an additional evaluation for an underlying etiology. The study site guidance for assessment and follow-up of these criteria can be found in the Investigator Study File Binder (or equivalent).

- 2. Complex sleep-related behaviors
- 3. Sleep paralysis (including sleep onset paralysis [adjudicated])
- 4. Hypnagogic or hypnopompic hallucinations
- 5. Somnolence resulting in discontinued intervention
- 6. Fall (adjudicated to rule out cataplexy)
- 7. Suicidal ideation, suicidal behaviors
- 8. Selected events associated with potential for abuse
- 9. Cataplexy (adjudicated)

CAC will adjudicate events, which occurred after randomization, of "cataplexy", "sleep onset paralysis" and "fall" reported by the investigators (For the details, see Section 10.1.4.1).

#### 8.5 Treatment of Overdose

In this study, an overdose is any dose higher than 15 mg per night (i.e., 1 tablet per night).

For the specific treatment for an overdose, see the IB/approved labeling.

Decisions regarding dose interruptions will be made by the investigator in consultation with the Sponsor based on the clinical evaluation of the participant.

#### 8.6 Pharmacokinetics

PK parameters will not be evaluated in this study.

#### 8.7 Pharmacodynamics

Pharmacodynamic parameters will not be evaluated in this study.

#### 8.8 Future Biomedical Research Sample Collection

Future biomedical research samples will not be collected in this study.

#### 8.9 Visit Requirements

Visit requirements are outlined in Section 1.3. Specific procedure-related details are provided in Section 8.

#### 8.9.1 Screening Period (from Screening until First Dose of Study Medication)

#### 8.9.1.1 Screening/Visit 1

After the documented informed consent from the participant, the investigator will review whether he/she meet the inclusion and does not meet exclusion criteria.

*Note: For participants hospitalized due to acute disease, APACHE II and ECOG PS will be assessed.* 

Note: For participants hospitalized due to elective surgery, the operative method (i.e., surgery requiring general anesthesia) will be confirmed.

After completing the above, the participants will be registered.

In case Visit 1 and Visit 2 occur on the same day, the overlapping procedures at both visits (e.g., reviewing the inclusion/exclusion criteria) specified in SoA should be performed only once.

In case Visit 1 and Visit 2 occur on different days, the procedures of Visit 1 and the randomization should be performed within 24 hours after admission for participants hospitalized due to acute disease, and the procedures of Visit 1 should be performed within 14 days before admission for participants hospitalized due to elective surgery.

## 8.9.1.2 Baseline/Visit 2 (until Randomization)

The qualified rater will assess DSM-5 and DRS-R-98 on the day of randomization. The participant will complete RCSQ.

After reviewing whether the participant meets the inclusion and does not meet exclusion criteria based on the above assessments, the eligible participant will be registered and randomized. In addition, the participant will receive appropriate non-pharmacotherapy based on his/her condition (See Section 5.3.1).

The received randomization number will be entered in the participant identification card. The study medication will be prescribed to the participant according to the Component ID. The investigator will instruct the participant to take one tablet of study medication once daily orally before bedtime from the day.

# 8.9.1.3 Visit 2 (from Randomization until First Dose of Study Medication)

Within 3 hours before the first dose of study medication, the qualified rater will assess DSM-5 again to confirm whether the participant does not develop delirium after randomization. If the assessment before randomization is performed within 3 hours before the first dose of study medication, the re-assessment after randomization is not needed.

If the participant has symptom suspected delirium after the rater assessed before the first dose of study medication, the rater will reassess DSM-5 based on the information to confirm whether the participant does not develop delirium. If the rater judges the participant develops delirium as assessed by DRM-5 or if the rater cannot deny that the participant develops delirium as assessed by DRM-5, the participant must be discontinued from the study without administering study medication.

After the rater assessed before the first dose of study medication, in the case that the participant did not have symptom suspected delirium or in the case that the rater assessed the participant had not developed delirium even if he/she had symptom suspected delirium, the study medication will be administered to him/her.

The investigator or the clinical research coordinator will enter whether the participant had initiated to take the study medication or not to IRT.

## 8.9.2 Assessment Period (from First Dose of Study Medication until Last Assessment Visit)

The qualified rater will assess the efficacy once daily in the morning at least from the day after the first dose of study medication. The participant will complete RCSQ once daily in the morning.

At the last visit, the procedures specified in SoA will be performed in addition to the above.

The clinical coordinator should make sure that the participant has the participant identification card when he/she is discharged.

#### 8.9.3 Follow-up Period

## 8.9.3.1 Follow-up Visit

Participants will be required to return to the clinical site 14±3 days after the last dose of study intervention for the follow-up visit. If the follow-up visit occurs less than 14 days after the last dose of study intervention, a subsequent follow-up telephone call should be made more than 14 days post the last dose of study intervention to determine if any AEs have occurred since the follow-up visit.

In the event any serious drug-related adverse event occurred later than 14 days after the last dose of study intervention, it will be subjected to the follow-up evaluation.

#### 9 STATISTICAL ANALYSIS PLAN

This section outlines the statistical analysis strategy and procedures for the study. If, after the study has begun, but prior to the database lock, changes are made to the primary hypothesis, or the statistical methods related to the hypothesis, then the protocol will be amended (consistent with ICH Guideline E-9). Changes to exploratory or other nonconfirmatory analyses made after the protocol has been finalized, but prior to the database lock, will be documented in a supplemental Statistical Analysis Plan (sSAP) and referenced in the Clinical Study Report (CSR) for the study. Post hoc exploratory analyses will be clearly identified in the CSR.

#### 9.1 Statistical Analysis Plan Summary

Key elements of the statistical analysis plan are summarized below; the comprehensive plan is provided in Sections 9.2-9.12.

Study Design Overview	A Phase 3 multicenter, randomized, placebo-controlled, double-blind clinical study to evaluate the efficacy and safety of MK-4305 (suvorexant) for reducing incidence of delirium in Japanese participants at high risk of delirium.
Treatment Assignment	Participants will be randomized to suvorexant or placebo in a 1:1 ratio, stratified by hospitalization reason (acute disease, elective surgery) and age category (<75 years, $\geq$ 75 years).
Analysis Populations	Efficacy: Full Analysis Set (FAS) Safety: All Participants as Treated (APaT)
Primary Endpoint(s)	Proportion of participants with delirium during the assessment period as assessed by DSM-5
Statistical Methods for Key Efficacy Analyses	The treatment difference in the proportion of participants with delirium during the assessment period as assessed by DSM-5, along with the corresponding 95% confidence interval (CI) and the p-value based on the Miettinen and Nurminen method [Miettinen O, et al. 1985], will be provided. The analysis will be stratified by hospitalization reason (acute disease, elective surgery) and age category (<75 years, ≥75 years). The Cochran-Mantel-Haenszel weight will be used to obtain stratum-adjusted proportion difference.

Statistical Methods for Key Safety Analyses	The analysis of safety results will follow a tiered approach. The tiers differ with respect to the analyses that will be performed. p-Values for treatment comparison (Tier 1), and treatment differences along with 95% CIs (Tiers 1 and 2), will be calculated based on the unstratified Miettinen and Nurminen method for the proportion of participants with respective events.		
Interim Analyses	There are no planned interim analyses for this study.		
Multiplicity	No multiplicity adjustment is planned as the study has a single primary hypothesis that will be addressed with a single comparison of two treatments using one endpoint.		
Sample Size and Power	A total of 200 participants will be randomized to suvorexant or placebo in a 1:1 ratio. The study will have a power of 90 (80) % with a two-sided significance level of 0.05 to detect a difference between treatments if the true proportion of participants with delirium in the suvorexant group is 11.6 (13.7) % compared to 30% in the placebo group. If there are occurrences of delirium after randomization but prior to the first dose of study medication, then the number of randomized participants will be increased to account for such participants.		

#### 9.2 Responsibility for Analyses/In-house Blinding

The statistical analysis of the data obtained from this study will be the responsibility of the Clinical Biostatistics department of the Sponsor.

This study will be conducted as a double-blind study under in-house blinding procedures. The official, final database will not be unblinded until medical/scientific review has been performed, protocol deviations have been identified, and data have been declared final and complete. The randomized allocation schedule(s) for study treatment assignment will be generated by a clinical schedule manager who is otherwise not involved in the study. Randomization will be implemented using IRT (or equivalent).

#### 9.3 Hypotheses/Estimation

Objectives and hypotheses of the study are stated in Section 3.

#### 9.4 Analysis Endpoints

Key efficacy and safety endpoints are listed below. The baseline value is defined as the last available measurement prior to the first dose of study medication.

#### 9.4.1 Efficacy Endpoints

The primary efficacy endpoint is the proportion of participants with delirium during the assessment period as assessed by DSM-5.

The secondary efficacy endpoints are:

1. Severity of delirium during the assessment period as assessed by DRS-R-98, defined as the maximum (i.e., worst) of total score among those obtained daily during the assessment period.

2. Proportion of participants with delirium during the assessment period assessed by DRS-R-98, defined as the proportion of participants with the maximum total score of 14.5 or greater during the assessment period.

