#### 1.2 Schema

The study design is depicted in Figure 1.

The last assessment visit is the next day after the last dose of study medication for the completed participants, OR the timing that the assessment is performed after decision of discontinuation of study medication for the discontinued participants. The assessment period is from the first dose of study medication to the last assessment visit.

Discon SM= Discontinuation of study medication, R = Randomization

- \* For the participant hospitalized due to acute disease, the randomization is performed within 24 hours after admission.
- † For the participant hospitalized due to elective surgery, the procedures of Visit 1 are performed within 14 days before admission.

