Surgery (Only for elective surgery)				X (Day 2 or Day 3)				For acute disease, the need for surgery, the timing of surgery and the operative method is not limited.

Study Period:	Screening	g Period	(Fr		sessment Per dose to last a	iod ssessment visit)	Follow-up Period	Notes
Visit Title:	Screening	Baseline		Last Assessment H		Follow-up	Screening Period: For the participant	
Visit Number:	1	2	2	3	4	Discontinuation of study medication	5	hospitalized due to acute disease, the randomization is performed within 24 hours after admission. For the
Visit Timing (Allowance): Efficacy	Acute disease: within 24 hours Elective surgery: within 14 days	Da Before Randomi- zation	y 1 After Randomi- zation	Day 2 to Day 7	The next day after last dose		14 days post last dose (± 3 days)	participant hospitalized due to elective surgery, the procedures of Visit 1 are performed within 14 days before admission . When Visit 1 and Visit 2 are the same day, the overlapping procedures at both visits (e.g., checking the inclusion/exclusion criteria) should be performed only once. If the allowance range is not described, the visit does not have the allowance.
Procedures								
DSM-5		Х	х	X (every day)	X	Х		Assess if the participant develops delirium after randomization and maximum of 3 hours prior to the first dose. If the assessment before randomization is performed within 3 hours before the first dose, the re-assessment after randomization is not needed. At Visit 3 and Visit 4, assess in the morning.
DRS-R-98		Х		X (every day)	X	Х	X	At Visit 3 and Visit 4, assess in the morning.
RCSQ		Х		X (every day)	Х	Х		In the assessment period, assess in the morning.

Study Period:	Screening	g Period	(Fr		sessment Per lose to last a	iod ssessment visit)	Follow-up Period	Notes
Visit Title:	Screening	Baseline	(11)			Assessment	Follow-up	Screening Period: For the participant
Visit Number:	1	2	2	3	4	Discontinuation of study medication	5	hospitalized due to acute disease, the randomization is performed within 24 hours after admission . For the

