## 7 DISCONTINUATION OF STUDY INTERVENTION AND PARTICIPANT WITHDRAWAL

#### 7.1 Discontinuation of Study Intervention

Discontinuation of study intervention does not represent withdrawal from the study.

As certain data on clinical events beyond study intervention discontinuation may be important to the study, they must be collected through the participant's last scheduled followup, even if the participant has discontinued study intervention. Therefore, all participants who discontinue study intervention prior to completion of the protocol-specified intervention period will still continue to participate in the study as specified in Section 1.3 and Section 8.9.3.

Participants may discontinue study intervention at any time for any reason or be discontinued from the study intervention at the discretion of the investigator should any untoward effect occur. In addition, a participant may be discontinued from study intervention by the investigator or the Sponsor if study intervention is inappropriate, the study plan is violated, or for administrative and/or other safety reasons. Specific details regarding procedures to be performed at study intervention discontinuation are provided in Section 8.1.13 and Section 8.9.3.

A participant must be discontinued from study intervention but continue to be monitored in the study for any of the following reasons:

- The participant or participant's legally acceptable representative requests to discontinue study intervention.
- Developing delirium as assessed by DSM-5

After randomization, when the qualified rater judges that a participant developed delirium as assessed by DSM-5.

• Adverse events

In the case that the investigator assesses that administration of the study medication should be discontinued due to the occurrence of adverse experiences.

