#### PRODUCT: MK-4305 PROTOCOL/AMENDMENT NO.: 085-03

Protocol Violation

It becomes inappropriate to continue study intervention as a result of a significant protocol deviation.

• Non-Compliance with Study Drug

When a participant has not agreed with or followed the instructions related to the study medication, or a study intervention is not initiated on the day of Randomization.

• In addition, the investigator and/or the Sponsor judges that participant should discontinue the study medications for any other reason.

Example: When a participant has either transferred to another hospital after the initiation of study medication and is no longer able to participate in the study.

The study procedures of assessment period after discontinuation from study intervention are not performed, since the objectives of this study is to investigate the efficacy of suvorexant on reduction in incidence of developing delirium.

Discontinuation from study intervention is "permanent." Once a participant is discontinued from study intervention, they shall not be allowed to restart study intervention.

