#### 9.5 Analysis Populations

#### 9.5.1 Efficacy Analysis population

The FAS population will serve as the primary population for the analysis of efficacy data in this study. The FAS population consists of all randomized participants who have at least one assessment of delirium by DSM-5 following administration of at least one dose of study medication. Occurrences of delirium after randomization but prior to the first dose of study medication will thus be excluded from the analysis.

A supportive analysis using the Per-Protocol (PP) population may be performed for the primary efficacy endpoint if there is a substantial number of protocol violators (>10% of FAS) that will be excluded from the PP population. The PP population excludes participants due to major deviations from the protocol that may substantially affect the results of the primary efficacy endpoint. Potential deviations that may result in the exclusion of a participant from the PP population include:

- Significant violation to the inclusion/exclusion criteria that may affect the results of the primary efficacy endpoint
- Missing assessment of delirium by DSM-5 at any time during the assessment period
- Treatment duration of less than 5 days, with the exception of discontinuation due to delirium as assessed by DSM-5
- Missed dose(s) of study treatment at any time during the trial
- Use of prohibited concomitant medications

The final determination on major protocol deviations, and thereby the composition of the PP population, will be made prior to the unblinding of the database and will be documented in a separate memo.

Participants will be included in the treatment group to which they are randomized for the analysis of efficacy data.

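### Does calling the worst DRS-R-98 score in all FAS participants severity of delirium make the first secondary endpoint wrong?

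*Combined protocol and SAP*

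**What the plan says.** Sections 1.1, 3 and 4.2.1.1 list severity of delirium by DRS-R-98 as a secondary endpoint, and each adds in brackets that it is the maximum of the daily totals. Section 9.4.1 gives the definition: "defined as the maximum (i.e., worst) of total score among those obtained daily during the assessment period". Nothing in it requires the participant to have had delirium.

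Table 5 assigns the endpoint to the FAS and the aligned rank test. Section 9.5.1 defines that set without regard to outcome: "The FAS population consists of all randomized participants who have at least one assessment of delirium by DSM-5", after at least one dose.

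The scoring window is set elsewhere. In Section 1.2, "The assessment period is from the first dose of study medication to the last assessment visit", and for those who stop drug that visit is "the timing that the assessment is performed after decision of discontinuation of study medication for the discontinued participants". Section 7.1 requires drug to stop "when the qualified rater judges that a participant developed delirium as assessed by DSM-5". It then says "The study procedures of assessment period after discontinuation from study intervention are not performed", with the reason "since the objectives of this study is to investigate the efficacy of suvorexant on reduction in incidence of developing delirium". The Schedule of Activities includes a DRS-R-98 at the discontinuation visit, inside the window, and another at follow-up, outside it.

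**The concern.** The label suggests a measure of how bad delirium is when it happens. The score is taken in everyone, and most participants are expected not to become delirious. If suvorexant prevents episodes but leaves those that occur just as severe, fewer high scores appear in the suvorexant arm and the test can be significant. Reported under its label, that result could be read as milder delirium.

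A second feature adds to the doubt. Daily rating stops once delirium is diagnosed, so a later peak is not recorded, and Section 7.1 justifies the stop by the incidence objective alone even though a severity objective is also stated.

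At stake is the reading of one secondary result. The primary endpoint, its test and its error rate are not involved.

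**Working it through.** **Inputs.** From Section 9.9.1: 100 per arm, two-sided 0.05, delirium in 30% on placebo and 11.6% (90% power) or 13.7% (80% power) on suvorexant. From Section 9.6.1: alignment within strata, then an unstratified rank-sum test. The documents give no DRS-R-98 means or spreads, so anything that depends on them is an assumption.

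**1. The plan's own figure.** With p0 = 0.30, p1 = 0.116 and mean 0.208, the null SE is √(2 × 0.208 × 0.792 / 100) = 0.0574. The SE under the alternative is √((0.30 × 0.70 + 0.116 × 0.884) / 100) = 0.0559. Power is Φ((0.184 − 1.96 × 0.0574) / 0.0559) = 0.90. At 13.7% it is 0.80. Both agree with Table 7. No power is stated for the severity endpoint.

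**2. Share of scores from non-cases.** This needs no score assumption.

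| Suvorexant / placebo | Non-cases of 200 | Share |
|---|---|---|
| 11.6% / 30% | 88.4 + 70 = 158.4 | 79% |
| 13.7% / 30% | 86.3 + 70 = 156.3 | 78% |
| 8.1% / 25% | 91.9 + 75 = 166.9 | 83% |
| 27.8% / 50% | 72.2 + 50 = 122.2 | 61% |

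**3. Effect on incidence only.** Let q be the chance that a case's worst score exceeds a non-case's, with identical episodes in both arms. Then P(placebo score > suvorexant score) = 0.5 + (p0 − p1)(q − 0.5). The null SE of this quantity is √(201 / (12 × 100 × 100)) = 0.0409. At q = 1 and 11.6% versus 30% it is 0.5 + 0.184 × 0.5 = 0.592, and the rejection rate is Φ(0.092 / 0.0409 − 1.96) = 61%.

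| q | 11.6% v 30% (simulated) | 13.7% v 30% (simulated) |
|---|---|---|
| 1 | 62% | 52% |
| 0.95 | 53% | 44% |
| 0.9 | 44% | 35% |
| 0.8 | 27% | 22% |
| 0.7 | 14% | 12% |

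The planned aligned rank test, simulated with four assumed sets of well-separated scores, gave 57% to 64% and 46% to 55% for the two designs. With no effect at all it gave 4.5% to 5.3%.

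**4. Effect on severity only.** Take 30% in both arms, every placebo case scoring above every suvorexant case, and all cases above all non-cases. Then P = 0.5 + 0.3 × 0.3 × 0.5 = 0.545, and the test is significant in about 20% of trials. The endpoint responds more to incidence than to severity among cases.

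**5. Does the stop in rating cause this?** No. With an incidence effect only and 0%, 5%, 10% or 20% of non-cases stopping early, the simulated aligned rank test rejected in 58%, 58%, 56% and 58% (simulation error about 1 point). The mixing comes from scoring everyone. The stop only means that the course after detection is not seen.

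**6. What a reader would see alongside it.** In the model of step 3, with q from 0.8 to 1 and either suvorexant rate, 92% to 98% of trials with a significant score result also had a significant primary result.

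**The case for a change.** The strongest case for a change is that the label recurs in the synopsis, the objectives, the rationale, the methods and Table 5, that Section 4.2.1.1 presents the scale as useful for grading severity, and that no sentence warns that occurrence and severity are combined. Renaming the endpoint and adding one interpretive sentence would need no new data. The mechanism needs only q above 0.5, which the plan itself relies on when it uses a score of 14.5 or more to identify delirium.

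The mechanism stands. The claim that the plan is wrong does not:

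- The label carries its definition. A reader of Section 3 is told that the endpoint is the maximum daily total, and nothing says it is severity among cases.
- Scoring every FAS participant is the sounder choice. A test among cases alone would compare groups formed by an outcome after randomisation.
- Non-cases' scores are still graded symptom data. Secondary endpoint 2 counts anyone reaching 14.5, whatever the DSM-5 finding.
- Sections 4.2.1.1 and 8.2.2 have each rating cover the time since the previous one, so the discontinuation rating takes in the interval up to detection. Later scores would be off study drug, and Section 6.5.1 then permits antipsychotics.
- Rewording the synopsis, Section 3 and Section 9 would mean a protocol amendment with ethics and regulatory submission (Section 10.1.1). The data, the analysis and the p-value would all stay the same.

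**Conclusion.** No change is needed; this is a fair trade-off. The endpoint combines occurrence of delirium with severity up to and including the discontinuation assessment, so lower incidence alone can produce a difference. About 79% of scores come from non-cases at the design rates, which is arithmetic from Section 9.9.1 with all 200 in the FAS. The 12% to 62% range in step 3 and the aligned rank results depend on assumed scores and are illustrative.

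The definition is complete, the test can be run as written and keeps its level, and Section 9.8 confirms that the only formal hypothesis is on the primary endpoint. Any harm would come from how a report words the result. Authors should call it the highest daily DRS-R-98 total and should not present a difference as proof of milder episodes. A descriptive table of the maximum score among DSM-5 cases by arm, marked as a non-randomised comparison, could sit in the supplemental SAP, to which Section 9.6.1 already leaves supportive analyses.
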